## **10.5 Documentation of Death and Reporting Requirements**

Deaths during treatment and the follow-up period, including death due to disease, will be recorded as an SAE and reported per [Section 10.6](#). Deaths due to disease should be recorded as a Grade 5 Neoplasm.

In addition, even after the follow-up period ends, the death date must be documented in the patient follow-up tab in [REDACTED] upon knowledge using the comment field in survival status section to record the cause.

## 10.6 Participating Sites Event Reporting Table

Event Type	Reporting Timeframe	Form to Use	Email to
Any event meeting the definition of serious	Within 24 hours of knowledge	Paper SAE Report Form	Masonic Cancer Center (MCC) Multisite Program Manager [REDACTED]
Dose Limiting Toxicity Event	Within 24 hours of knowledge	DLT Event Form	
Stopping Rule Event	Within 24 hours of knowledge	Stopping Rule Event Form	
Major Deviations, as defined in Section 10.1 .	Within 5 working days of knowledge	Record in Deviations Tab, generate report and have PI sign	
Minor Deviations, as defined in Section 10.1 .	Reporting not applicable	Record in Deviations Tab – signed report not required	Not applicable

Participating Sites are responsible for reporting to Local institutional IRB or other entities per institutional policies and guidelines.

The Multisite Program Manager will forward all reports to GT Biopharma and [REDACTED] within 3 business hours.

GT Biopharma/[REDACTED] is responsible for submission of IND safety reports to the FDA per federal regulations.

## 10.7 UMN Required Reporting: UMN IRB, GT Biopharma, [REDACTED], and Masonic Cancer Center's SAE Coordinator

Entity Reported To:	Criteria for reporting	Timeframe	Form to Use	Report to
U OF MN IRB	Information that indicates a new or increased risk, or safety issue. Unexpected Death per UMN requirements.	5 business days	Ethos Reportable New Information (RNI)	Via [REDACTED] with copy GT Biopharma*
	Clinical deviations per current IRB reporting requirements (UMN patients only)		[REDACTED] Deviation Report and [REDACTED]	
GT Biopharma and [REDACTED]*	Any event meeting the definition of serious regardless of attribution	Within 24 hours of knowledge	CTO SAE Report Form	GT Biopharma and [REDACTED]
	Events that count toward dose limiting toxicity during the dose finding component or an early study stopping rule during the expanded component	At time of reporting	Appropriate form	

\*GT Biopharma/[REDACTED] is responsible for submission of IND safety reports to the FDA per federal regulations.

## 11 Study Data Collection and Monitoring

### 11.1 Data Management

This study will collect regulatory and clinical data using [REDACTED]  
[REDACTED]

The [REDACTED] database resides on dedicated secure and PHI compliant hardware consisting of 3 physical servers: dev, DR, and production. All the data servers are managed by the [REDACTED] All relevant [REDACTED] procedures related for PHI compliant servers (as required by the Center of Excellence for HIPAA Data) apply to [REDACTED] databases.

The integrated data will be stored in PHI compliant servers managed by [REDACTED] with access given to those authorized users in the Clinical and Translation Science Institute Informatics team (CTSI BPIC and MCC CISS).

[REDACTED]  
[REDACTED]

Key study personnel are trained on the use of [REDACTED] and will comply with protocol specific instructions embedded within the [REDACTED].

### 11.2 Case Report Forms

Participant data will be collected using protocol specific electronic case report forms (e-CRF) developed [REDACTED] based on its library of standardized forms. The e-CRFs will be approved by the lead center PI and the UMN biostatistician prior to release for use. The Study Coordinator or designee will be responsible for registering the patient into [REDACTED] at time of study entry, completing e-CRF based on the patient specific calendar, and updating the patient record until patient death or end of required study participation.

### 11.3 Data and Safety Monitoring

The study will be in compliance with the [REDACTED]  
[REDACTED]

The site PI will comply with at least twice yearly monitoring of the project by their site's internal monitoring staff. Monitoring reports are forwarded to the U of MN Multisite Program Manager who will forward to the reports to GT Biopharma [REDACTED]

[REDACTED] Refer to the Procedures Manual for Participating Sites for additional information.

All sites must permit study-related monitoring, audits, and inspections by the IND Sponsor (GT Biopharma and/or their designee), IRB, government regulatory bodies, and compliance groups. The investigator will make available all study related documents (e.g. source documents, regulatory documents, data collection instruments, study data, etc.). The investigator will ensure the capability for inspections of applicable study-related facilities (e.g. pharmacy, diagnostic laboratory, etc.) will be available for trial related monitoring, audits, or regulatory inspections.

#### **11.4 UMN Led Teleconferences – Participating Sites, GT Biopharma** [REDACTED]

[REDACTED] Regular teleconferences will be held to facilitate communication between the participating sites and IND sponsor/representative regarding the study's progress, including patient updates, a summary of safety reports, dose level/patient slot availability, case report form completion, and other issues for discussion. The Masonic Cancer Center Multisite Program Manager is responsible for arranging these teleconferences and preparing the agenda. Meetings occur every 2 weeks; however, they may be scheduled more or less frequently at the discretion of the lead institution. Participation of a minimum of one representative from each participating clinical site is expected. Attendance by [REDACTED] GT Biopharma is agenda driven.

These teleconferences are in addition to other previously described site interactions including centralized patient registration, institutional and MCC required reporting of safety related issues, and case report form completion in the study's central database [REDACTED]

#### **11.5 Record Retention**

The investigator will retain essential documents (e.g. study records including source data, copies of case report form, consent forms, HIPAA authorizations, and all study correspondence) until at least 2 years after the last approval of a marketing application in an ICH region and until there are no pending or contemplated marketing applications in an ICH region or at least 2 years have elapsed since the formal discontinuation of clinical development of the investigational product. These documents should be retained for a longer period

however if required by the applicable regulatory requirements or by an agreement with the sponsor.

It is the responsibility of the sponsor (GT Biopharma) to inform the investigator/institution as to when these documents no longer need to be retained.

## 12 Statistical Considerations

### 12.1 Study Design and Endpoints

This is a multisite Phase I/II study of GTB-3550 trispecific killer cell engager (TriKE) for the treatment of high risk MDS and relapsed AML. Once the MTD is identified, the objective will be to confirm safety and obtain preliminary estimates of efficacy as measured by the objective response, the **primary trial endpoint** as assessed between Day 21 and Day 42. For AML clinical response includes complete remission with or without hematologic or platelet recovery (CR, CRi or CRp) or partial response. For MDS clinical response includes complete remission, marrow CR (with incomplete peripheral blood count normalization), partial response or hematologic improvement (HI). For advanced systemic mastocytosis response is considered a decrease in mast cell burden in bone marrow or serum tryptase level by at least 30%.

All patients completing Block #1 will be evaluable for DLTs and toxicities. Patients who discontinue therapy prior to completion of both Block #1 and Block #2 will be replaced. Patients completing Block #1 and Block #2, but come off treatment for disease progression, will still be evaluable for efficacy and will not be replaced. If needed a subgroup of patients receiving all 3 blocks will also be evaluated for response as a secondary population. We expect that the number of patients coming off therapy after only completing block #1 will be minimal.

**Secondary trial endpoints** will include toxicity through Day 29 and overall survival (OS) at 6 months from 1st dose of study drug.

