## 1 Objectives

### 1.1 Primary Objective

Phase I Dose Finding: To identify the maximum tolerated dose (MTD) of GTB-3550 TriKE defined as the dose level that most closely corresponds to a dose limiting toxicity rate (DLT) of 20%.

Phase II Extension: To determine preliminary efficacy as measured by the rates of “best” clinical response by Day 42 after the start of the 1st infusion.

For AML clinical response includes complete remission with or without hematologic or platelet recovery (CR, CRi or CRp) or partial response. For MDS clinical response includes complete remission, marrow CR (with incomplete peripheral blood count normalization), partial response or hematologic improvement (HI). For advanced systemic mastocytosis response is considered a decrease in mast cell burden in bone marrow or serum tryptase level by at least 30%.

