### 5.1 Eligible Diseases

Diagnosis of one of the following CD33-expressing myeloid malignancies with greater than or equal to 50% CD33+ target cells with no good standard of care treatment options including:

High Risk Myelodysplastic Syndromes (MDS) progressive on two or more prior regimens and requiring treatment that meets **at least one** of the following:

- IPSS-R High or Very High Risks
- WHO Classification: RAEB-1 or RAEB-2
- Poor and very-poor risk cytogenetic abnormality as defined by the IPSS-R cytogenetic classifications
- WHO Based Prognostic Scoring System (WPSS): High or Very High Risk

Therapy related MDS and not a candidate for induction chemotherapy or had an inadequate treatment response after induction chemotherapy.

Refractory or Relapsed Acute Myelogenous Leukemia (AML) meeting **at least one** of the following:

- Refractory AML defined as failure to achieve remission after at least 3 induction attempts
  - Elderly AML not fit for induction therapy can be enrolled after 2 failed inductions
- Relapsed AML
  - Not a candidate for hematopoietic stem cell transplant (HSCT), at least one re-induction attempt required
  - Prior HSCT relapse beyond 3 months may be included only if off immunosuppression for a minimum of 4 weeks and do not have GVHD

Notes:

- 1) For hypomethylating agents (i.e. decitabine, azacitidine) to count as an induction/re-induction attempt, the patient must have completed a minimum of 3 monthly cycles
- 2) For targeting agents (i.e. sorafenib) to count as an induction/re-induction attempt, the patient must have completed a minimum of 1 month without attaining CR

Advanced systemic mastocytosis (defined as mast cell leukemia, aggressive systemic mastocytosis, and systemic mastocytosis associated with hematologic neoplasm) may enroll without any prior treatment, given there is no standard established therapy.

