#### **7.1.5 Criteria to Continue with GTB-3550 TriKE Block #2 and #3**

A dose limiting toxicity (for any patient, not just dose finding) during the previous block's infusions (defined in [Section 7.2.1](#)) will disqualify a patient from receiving further therapy.

**Disease based treatment decisions:** If after completing Block #1 and Block #2, the patient has clear evidence of disease progression they will be discontinued from study treatment and further treatment with study drug is to be discontinued. Such patients remain fully evaluable for efficacy and toxicity.

To begin a new block, on the day of the planned treatment the patient must:

- not currently meet any disease specific hematologic dose limiting toxicity as defined in [Section 7.2.1](#).
- have an estimated glomerular filtration rate  $\geq 60$  mL/min/1.73 m^2
- have a total bilirubin of  $\leq 1.5$  times the ULN

- have AST and ALT  $\leq$  3 x upper limit of normal, and alkaline phosphatase levels  $\leq$  2.5 x upper limit of normal
- be afebrile (defined as a temperature of  $\leq$  101°F)
- have room air O2 saturation  $\geq$  88%
- have a blood pressure  $\geq$  100/65 mm/Hg
- have no signs or symptoms of infection

If the above criteria is not met, treatment must be delayed for appropriate supportive care and clinical assessment. The study drug may begin the following day, if the above criteria are met and, in the opinion of the clinical provider it is safe to proceed. Otherwise delay 1 week from the planned start and reassess at that time.

Patients unable to begin treatment after a 1 week delay will be permanently discontinued from treatment and followed per [Section 7.6](#).

The start of Block #2 or Block #3 may be delayed for up to 1 week (i.e. start 1 week later than planned) to allow for the resolution of any treatment or non-treatment issues (i.e. URI, UTI, etc.) or for holiday/scheduling issues.

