### **Myelodysplastic Syndromes (MDS):**

Category	Response criteria (responses must last at least 4 wk)
Complete remission	
Bone marrow: <math>\leq</math> 5% myeloblasts with normal maturation of all cell lines*
 
 
• Persistent dysplasia will be noted*†
 
 
Peripheral blood‡
 
 
• Hgb <math>\geq</math> 11 g/dL
 
• Platelets <math>\geq</math> 100 <math>\times</math> 10^9/L
 
• Neutrophils <math>\geq</math> 1.0 <math>\times</math> 10^9/L†
 
• Blasts 0%
 

Partial remission	
All CR criteria if abnormal before treatment except:
 
 
• Bone marrow blasts decreased by <math>\geq</math> 50% over pretreatment but still <math>></math> 5%
 
 
Cellularity and morphology not relevant

Marrow CR	
Bone marrow: <math>\leq</math> 5% myeloblasts and decrease by <math>\geq</math> 50% over pretreatment†
 
Peripheral blood: if HI responses, they will be noted in addition to marrow CR†

Stable disease	
Failure to achieve at least PR, but no evidence of progression for <math>\geq</math> 8 weeks

Cytogenetic response	
Complete
 
 
• Disappearance of the chromosomal abnormality without appearance of new ones
 
 
Partial
 
 
• At least 50% reduction of the chromosomal abnormality
 

Hematologic Improvement	
Erythroid response (pretreatment, < 11 g/dL): Hgb increase by 1.5 g/dL Relevant reduction of units of RBC transfusions by an absolute number of at least 4 RBC transfusions/8 wk compared with the pretreatment transfusion number in the previous 8 wk.
 
Platelet response (pretreatment, < 100 X 10^9/L): Absolute increase of < 30 X 10^9/L for patients starting with 20 X 10^9/L platelets Increase from less than 20 X 10^9/L to greater than 20 X 10^9/L and by at least 100%
 
Neutrophil response (pretreatment, < 1.0 X 10^9/L) At least 100% increase and an absolute increase 0.5109/L

MDS indicates myelodysplastic syndromes; Hgb, hemoglobin; CR, complete remission; HI, hematologic improvement; PR, partial remission; FAB, French-American-British; AML, acute myeloid leukemia; PFS, progression-free survival; DFS, disease-free survival.

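### The mastocytosis response rule ignores the associated blood cancer, so a patient whose associated neoplasm is progressing can be counted as a responder

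*Combined protocol and SAP*

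**What the plan says.** **The rule.** Sections 1.1 and 12.1 and the Synopsis give the same one-sentence rule for mastocytosis. In 12.1 it reads: "For advanced systemic mastocytosis response is considered a decrease in mast cell burden in bone marrow or serum tryptase level by at least 30" percent. Either marker is enough, and no other condition is attached.

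**Who is eligible.** Section 5.1 lists "Advanced systemic mastocytosis (defined as mast cell leukemia, aggressive systemic mastocytosis, and systemic mastocytosis associated with hematologic neoplasm", so some of these patients have a second blood cancer.

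**Progression.** Section 7.1.5 takes patients who are clearly progressing after Blocks 1 and 2 off study treatment and adds: "Such patients remain fully evaluable for efficacy and toxicity". Section 12.1 agrees: patients who complete both blocks "but come off treatment for disease progression, will still be evaluable for efficacy" and are not replaced.

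**Timing.** Section 12.1 describes the primary endpoint "as assessed between Day 21 and Day 42". Section 1.1 takes the best response by Day 42.

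**Detailed criteria.** Appendix III covers acute leukemia and MDS only. Its duration requirement ("responses must last at least 4 wk") heads the MDS table.

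**Measurement.** Section 8.1 schedules a disease assessment and marrow biopsy at screening and between Days 21 and 42. Tryptase appears in none of the tables in 8.1, 8.2 or 8.3.

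**Use.** Sections 12.1 and 12.3 pool all diseases: go on to Stage 2 with at least 3 responders of 13, and call the drug promising with 10 of 30.

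**The concern.** A response rule should not be satisfied while the patient's cancer is getting worse. In mastocytosis with an associated neoplasm, the mast cell component and the other neoplasm can move in different directions, and the rule looks at only one of them. A patient can be withdrawn for progression and still be a responder, because staying evaluable means being scored, and the only scoring rule available is the marker rule.

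Such a patient then counts the same as an AML remission or an MDS response. The thresholds are low enough that one patient can decide whether Stage 2 opens or whether the drug is carried forward. With up to 10 sites, each would have to settle for itself whether progression overrides a marker fall, and when tryptase is read.

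**Working it through.** **Step 1: follow the text for one patient.** The values are invented to trace the rules.

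1. The patient has mastocytosis with an associated neoplasm: eligible under 5.1.
2. Tryptase falls from 60 to 40: (60 − 40)/60 = 33%, which is at least 30%, so the rule in 12.1 is met.
3. Marrow blasts of the associated neoplasm rise from 8% to 25%, and the patient is taken off treatment after Block 2 under 7.1.5.
4. Under 7.1.5 and 12.1 the patient stays evaluable for efficacy.
5. No sentence in 1.1, 7.1.5, 12.1 or Appendix III cancels the response.

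Result: responder. This needs no assumption about measurement error. If progression is first seen on the Day 21 to 42 marrow instead, steps 2 and 5 give the same result.

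**Step 2: the plan's own design.** Inputs from 12.1 and 12.3: 13 then 17 patients; continue with at least 3; success with at least 10 of 30; 20% versus 40%; 80% power; significance level 0.05. Let X1 be binomial(13, p) and X2 binomial(17, p).

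- P(Stage 2) at p = 0.2 is 1 − P(0) − P(1) − P(2) = 1 − 0.0550 − 0.1787 − 0.2680 = 0.498.
- P(success) is the sum over x ≥ 3 of P(X1 = x) × P(X2 ≥ 10 − x). This gives 0.0577 at p = 0.2 and 0.805 at p = 0.4.

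The stated power is reproduced. The exact error rate is 5.8% rather than 5%; that is a separate matter, and 5.8% is used below only as the reference value.

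**Step 3: one miscounted responder in Stage 1.** One of the 13 is a certain responder, and the other 29 patients respond at 20%. Let Y be binomial(12, 0.2).

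- P(Stage 2) = P(Y ≥ 2) = 1 − 0.0687 − 0.2062 = 0.725.
- P(success) is the sum over y ≥ 2 of P(Y = y) × P(X2 ≥ 9 − y) = 0.106.

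| At a true 20% rate | Reach Stage 2 | Declare success |
|---|---|---|
| Design as stated | 49.8% | 5.8% |
| One certain miscount in Stage 1 | 72.5% | 10.6% |

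This shows what one error does. It does not show how often the rule produces one.

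**The case against.** **The subgroup may be very small.** The documents neither state nor cap the number of mastocytosis patients, and 12.1 introduces the study as one in MDS and AML. With no such patient the gap has no effect. This stands, and it limits the size of the concern but not the defect in the rule.

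**The table assumes the error.** Any forced responder, in any disease, would give the same figures. This also stands, so they are an illustration only.

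**A reader might go further and infer that measurement noise alone is scored as response and inflates the error rate by a known amount.** The rule sets no minimum baseline, so noise can add false responses, but the documents give no within-patient variability. Assume lognormal error, no true change, one reading of each marker and independent markers. The chance that one marker falls by 30% is then Φ(ln 0.7 / √(2 ln(1 + CV²))). A CV of 10% on both markers gives 0.6% each, and 1 − (1 − 0.0057)² = 1.1% for either. A CV of 30% gives 19.5% each, and 1 − (1 − 0.195)² = 35% for either. A range that wide is no estimate. Nor must noise inflate the pooled result: if these patients were scored responders at a rate below the 20% null, they would lower it.

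**A reader might also infer that no baseline is needed, or that a repeat value is plainly missing.** A decrease implies a baseline value, and a screening marrow is scheduled; only a minimum level is absent. AML responses in Appendix III carry no stated repeat or duration either, so asking for confirmation in mastocytosis alone would be a preference and not a correction.

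**Tryptase may be meant to fall under the generic disease assessment rows in 8.1.** That is possible, but the tables do not say so, and half of the endpoint should not rest on an inference.

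**Conclusion.** The concern holds for the associated neoplasm. The rule, the eligibility definition, the evaluability clause and the absence of mastocytosis criteria in Appendix III together allow a progressing patient to be counted as a responder. This follows from the text alone.

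How often it would happen cannot be derived. The illustrated effect of one miscount (50% to 73% for reaching Stage 2, 5.8% to 10.6% for success) assumes a certain error in Stage 1, a true 20% rate in everyone else, and the 13 + 17 design, which 12.1 would adjust if Phase I places more than 13 patients at the MTD.

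The missing minimum baseline and the unscheduled tryptase are real but lesser gaps, and their effect cannot be estimated from the documents. The point deserves correction before responses are read, but it does not put the design as a whole in doubt.

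**What to change.** Change the scoring only, not treatment or its stopping.

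1. Add a mastocytosis section to Appendix III and cite it in 1.1 and 12.1. State that a patient whose associated neoplasm progresses by Day 42, or who is stopped for progression under 7.1.5, is counted as a non-responder and stays in the denominator. Say there how progression of the associated neoplasm is judged, since Appendix III contains no progression criterion.
2. List serum tryptase in the schedule at screening and at the Day 21 to 42 disease assessment, so that this half of the endpoint has a defined baseline and reading time.

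The cost is protocol wording and a tryptase assay at two time points in the mastocytosis patients. The downside is slightly fewer responders.

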### **7.1 GTB-3550 TriKE Administration**

Patients receive a single course of GTB-3550 TriKE at their assigned dose as 3 weekly treatment blocks. Each block consists of four consecutive 24 hour

continuous infusions (over approximately 96 hours) of GTB-3550 TriKE followed by a 72 hour break after Block #1 and #2. All treatment is given as an inpatient.

The assigned dose will be calculated on a weight obtained within 5 days prior to or on day of the 1st dose. The dose is not be recalculated for subsequent treatment blocks.

The institutional Investigational Pharmacy will prepare each 24 hour bag for infusion per [Section 9.6](#) based on the patient's assigned GTB-3550 TriKE dose. Each assigned dose will be administered as a 100 mL infusion over 24 hours period at 4.17 mL/hour rate. Note: actual bag volume is 130 ml to allow for the product sample collection before and after infusion.

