**Infusion Related Reactions:**

If Grade 2 infusion related reaction occurs, interrupt the infusion and treat symptomatically with antihistamines, NSAIDS, narcotics, IV fluids as medically appropriate. Any patient experiencing a second Grade 2 infusion related reaction after restarting, despite pre-medication or a Grade 3 or 4 infusion related reaction will be permanently discontinued from GTB-3550 TriKE.

Administration of glucocorticoids is prohibited during the TriKE treatment period as the use of systemic steroid medications may result in loss of therapeutic effects of the study drug. They should be avoided except in the event of a severe toxicity.

Any Grade 3 or 4 infusion related reaction will result in permanent discontinuation of study drug with appropriate medical intervention.

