    - Grade 4 platelet count (<25,000/ $\mu$ L) lasting  $\geq$  29 days from start of cycle in the absence of active MDS/Mast cell disease
    - Any clinically significant bleeding that is not controllable with transfusion support
    - Grade 4 anemia, unexplained by the underlying disease

- Grade 3 infusion related, treatment related reaction including cytokine release syndrome which does not resolve within 72 hours despite best medical management (refer to [Section 10](#) for modified CRS grading)
- Grade 3 or 4 Tumor Lysis Syndrome that does not resolve within 7 days with or without intervention
- Inability to complete at least one block of three 24 hour infusions due to any treatment emergent, treatment related toxicity.

**Maximum Tolerated Dose (MTD)** is defined as the dose level that most closely corresponds to the target DLT rate of 20%.

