## 10.2 Event Documentation

Event monitoring and documentation begins with the 1st dose of TriKEs.

For the purposes of this study, selected expected adverse events will be assessed using the Targeted Toxicity Worksheet ([Appendix VI](#)) and any unexpected events will be collected at the following time points in relation to the GTB-3550 TriKE infusions through Day 29:

- Prior to the infusion start of each 24 hour infusion (i.e. Day 1, 2, 3, 4, and Day 8, 9, 10, 11, and Day 15, 16, 17, 18)
- At the end of the final infusion of each block (i.e. Day 5, Day 12, Day 19)
- Day 22
- Day 29

At each time point, the worst grade of the targeted toxicity since the last assessment or the previous 24 hours (whichever is shorter) will be recorded in addition to any unexpected toxicities felt at least possibly related the study treatment.

If a patient discontinues study therapy early or otherwise does not receive treatment as planned, the targeted toxicity assessment time points may be adjusted or eliminated; however, patients must be assessed for a minimum of 28 days from the 1st dose of study drug.

If a patient is not abiding by the standard of care study calendar ([Section 8.1](#)), collection of the corresponding targeted events (and research related samples) also may be altered or discontinued on an individual patient basis, as appropriate.

Monitoring for adverse events will end after the last targeted assessment; however, the investigator is obligated, upon knowledge of, to report any event meeting the criteria in [Section 10.5](#).

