## 12.2 Statistical Analysis

Response will be estimated with simple proportions and descriptive plots. The secondary endpoint of OS will be estimated with Kaplan-Meier curves. Safety measures will be described with frequencies and proportions.

The change in number, phenotype and function of NK cells from baseline to the end of treatment will be correlated with clinical response using appropriate regression analyses such as Cox or Logistic regression. Assessment of serum TriKE levels will be determined using descriptive statistics.

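### Section 12.1 ties toxicity evaluability to completing Block #1 and no all-treated safety set is defined, so patients stopped by early toxicity can drop out of the Day 29 toxicity rates

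*Combined protocol and SAP*

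**What the plan says.** Section 12.1 gives the evaluability rule: "All patients completing Block #1 will be evaluable for DLTs and toxicities". The next sentence adds that "Patients who discontinue therapy prior to completion of both Block #1 and Block #2 will be replaced", with no exception for patients who stop because of toxicity. The same section says the secondary endpoints "will include toxicity through Day 29 and overall survival (OS) at 6 months". Section 12.2 adds only that "Safety measures will be described with frequencies and proportions", without naming the patients who form the denominator.

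The treatment plan makes completion of Block 1 depend on toxicity. Under Section 7.1, "Any Grade 3 or 4 infusion related reaction will result in permanent discontinuation of study drug with appropriate medical intervention", and a second Grade 2 reaction after restarting has the same result. Under Section 7.3.3, a Grade 3 liver test elevation ends the current block and the missed doses are not made up.

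Data collection is wider than the evaluability rule. Section 10.2 says "Event monitoring and documentation begins with the 1 st dose of TriKEs", and patients who stop early must still be assessed for at least 28 days from the first dose. Sections 7.2.1 and 10.3 list as a DLT: "Inability to complete at least one block of three 24 hour infusions due to any treatment emergent, treatment related toxicity". Section 7.1 describes a block differently: "Each block consists of four consecutive 24 hour" infusions.

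**The concern.** A safety set should be fixed by exposure. A set fixed by finishing the first block is fixed by an outcome, because patients who tolerate the drug poorly are the ones who do not finish. If the sentence in Section 12.1 serves as the definition of the toxicity set, most Grade 3-4 infusion related reactions in Block 1 would fall outside the table meant to describe them. This agent's expected toxicities come from immune activation (Section 9.7), so the first infusions matter most for safety.

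At stake are the secondary toxicity endpoint and the safety tables of both components. The same clause also covers DLTs. A literal reader could therefore remove from the CRM a patient whose early toxicity the DLT definition is written to capture.

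**Working it through.** **1. Is the sentence a definition?** It does not contain the word 'only'. Four places nevertheless treat evaluability as a status that sets a boundary or can be lost:
- The revision history (revision 9) describes the added text as defining who is evaluable.
- Section 7.1.5 reassures the reader that patients who progress after Blocks 1 and 2 stay evaluable for efficacy and toxicity.
- Section 7.2.1 accrues to 30 evaluable patients.
- Section 7.6 follows evaluable patients for survival.

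No section defines another toxicity set. The restrictive reading is therefore open, and no other denominator is stated to replace it.

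**2. The plan's own toxicity figures.** The nearest stated figures are in Section 12.4: a stopping probability of at most 10% at a true 10% rate, and 88% at a true 30% rate. The boundary is 2/3, 3/8, 4/13, 5/20, 6/26 or 7 events, with 27 patients. An exact patient-by-patient binomial recursion, stopping when events reach the boundary, gives 9.7% and 87.8%. Both stated figures reproduce.

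**3. Effect on a reported rate.** Let q1 be the proportion stopped by toxicity in Block 1 and q2 the toxicity rate among the rest. The documents give neither, so both are assumptions.
- All treated: q1 + (1 − q1) × q2
- Completers only: q2
- Expected number left out per 30 treated: 30 × q1
- Chance that at least one of 30 is left out: 1 − (1 − q1)^30

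With q2 = 10%:

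| q1 | All treated | Completers only | Left out of 30 | Chance of at least one |
|---|---|---|---|---|
| 5% | 0.05 + 0.95 × 0.10 = 14.5% | 10% | 1.5 | 78.5% |
| 10% | 0.10 + 0.90 × 0.10 = 19.0% | 10% | 3.0 | 95.8% |
| 15% | 0.15 + 0.85 × 0.10 = 23.5% | 10% | 4.5 | 99.2% |
| 20% | 0.20 + 0.80 × 0.10 = 28.0% | 10% | 6.0 | 99.9% |

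The completers' figure does not move, whatever happens in Block 1.

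**4. Which events are caught elsewhere?**
- Phase I: an early event that meets the DLT criteria is reported as a DLT. A Grade 3 infusion reaction that resolves within 72 hours does not meet the infusion-reaction criterion. If it occurs in the fourth infusion, the inability-to-complete criterion, worded for three infusions, may not be met either. Read literally, such an event could be neither a DLT nor in the toxicity set.
- Phase II: Section 10.3 reports DLTs for Phase I patients only. The toxicity stopping rule (10.4, 12.4) counts Grade 4-5 events only. Serious events are reported within 24 hours (10.6, 10.7). Non-serious Grade 3 reactions are what remains.

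**5. Why Section 12.4 merits a clarification.** It contains no completion condition, so this step is illustration only. Suppose a share s of a true 30% toxicity rate fell on Block 1 non-completers who were dropped and replaced. The rate among those counted would be (0.30 − 0.30s)/(1 − 0.30s). For s = 25%, 50% and 75% that is 24.3%, 17.6% and 9.7%. The stopping probability would then be 71%, 41% and 9%, instead of 88%.

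**The case against.** The strongest reply is that the sentence gives a sufficient condition and is silent on non-completers. Much of the protocol fits an inclusive reading. Events are recorded from the first dose, with at least 28 days of assessment. Inability to complete a block because of toxicity is itself a DLT. The Phase II stopping rules run from the start of treatment with no completion condition. Section 12.2 does not limit the safety tables to evaluable patients. The paragraph in 12.1 is also largely about replacement and accrual. All of this stands. It shows that the data will exist and that exclusion is not certain. It does not supply a denominator for the secondary endpoint.

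A reader might infer more: that 12.1 admits only completers, drops everyone stopped by toxicity in Block 1, and makes Grade 3-4 infusion reactions in that block zero by construction. The documents do not support this. The word 'only' is absent. Even under the restriction, a reaction at or after the end of the last bag can occur in a completer, and Section 7.3.5 lets a patient with Grade 3 hypoxia finish the hung bag, so that patient may complete Block 1 and then stop.

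A reader might also say that a completers-only confidence interval would exclude the true rate. That depends on pooling and on an assumed size. The exact 95% upper limit for 0/n is 1 − 0.025^(1/n). If 6 of 60 patients were dropped, 0/54 gives 6.6%, below an assumed true rate of 10%. If 3 of 30 were dropped, 0/27 gives 12.8%, which does not exclude 10%. Section 12.3 expects about 44 patients and at most 57.

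**Conclusion.** The point holds as a gap in the analysis set; data collection is adequate. The only toxicity set the plan states is conditioned on completing Block 1, and completion depends on toxicity. Applied as a definition, it can exclude patients stopped during Block 1, including most Grade 3-4 infusion related reactions in that block, and so understate the Day 29 toxicity rates. If the sentence is instead read as silent on non-completers, the denominator of a secondary endpoint is undefined and the same correction is needed.

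The size rests on two assumed rates. Across the range shown, the understatement runs from 4.5 percentage points (14.5% against 10%) to 18 points (28.0% against 10%). If toxicity rarely stops patients in Block 1, the effect is small; Section 12.1 expects few patients to come off after Block 1 alone but says nothing about stopping within it. Section 12.4 is not itself defective on this point.

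**What to change.** In Section 12.1, separate the sets:
- State that all patients who receive any amount of GTB-3550 are included in the toxicity analyses, by assigned dose level.
- As a clarification, state that all treated Phase II patients count in the events and denominators of the Section 12.4 stopping rules.
- State that a patient with a DLT before the end of Block 1 is DLT-evaluable and stays in the CRM data, whether or not that patient is replaced for efficacy. DLT evaluability should not be restricted to Block 1 completers. That would contradict the inability-to-complete criterion and could remove early DLTs from the CRM.
- Reconcile the four infusions per block in Section 7.1 with the three in the DLT criterion of Sections 7.2.1 and 10.3, so that completing Block #1 has one meaning throughout.

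The cost is a few sentences in 12.1 and one reconciliation. No new data or patients are needed, because events are already recorded from the first dose and early discontinuers are already assessed for at least 28 days.
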